### Measures.

**Sleep (Actigraphy).** Sleep will be monitored using an activity tracker watch (FitBit Charge 5, FitBit Inc., San Francisco, CA). Fitbits demonstrate superior accuracy and sensitivity with minimal bias compared to other models. The Charge 5 is the most recent model. Data will be downloaded via the FitBit app onto an IRB-approved and HIPA compliant research iPad. The following outcome measures will be calculated: total sleep duration and wake after sleep onset, two outcomes that are considered good indicators of sleep quality.

**Sleep (Resting State EEG).** Resting state EEG will be collected on test days to assess the waking effects of sleep quality. The primary outcome variable will be alpha power (8-12 Hz), which reflects a state of eyes closed wakeful rest. Decreasing alpha during eyes closed is an indicator of entry into early sleep stages when drowsy. As such, eyes closed alpha power is decreased after sleep deprivation and negatively correlated with sleepiness. Importantly, differing results can be observed for eyes open and eyes closed conditions, with more alpha during eyes open indicating sleepiness (which is the opposite to eyes closed). Therefore, both eyes open and eyes closed conditions will be measured and analyzed separately. Resting alpha power will be collected at each test day. See [EEG Protocol](#) for details.

**Sleep (Self-Report).** The PSQI is a well-validated and reliable measure of sleep quality. We will use the total summary score of the 18-items as the main outcome variable. We will also use the ISS and PROMIS-SF as secondary self-reported measures of sleep.

**Stress (Physiological).** The cold pressor task will be used to induce and measure the stress response. The cold pressor task reliably activates the sympathetic nervous system and the HPA axis which is observed by increases in heart rate, blood pressure, and cortisol. HPA-axis activation during the CPT can be increased by incorporating a social evaluative component. These will include 1) a study member dressed in a white labcoat and taking notes on a clipboard; and 2) a webcam and monitor showing the participant's face (no recording will actually be taken). Participants will be informed that their facial expressions will be assessed during the CPT. The addition of these social components during the CPT has been demonstrated to selectively activate the HPA-axis and significantly increase salivary cortisol levels. During the CPT, participants will submerge their dominant arm in an ice-water bath for up to 2 minutes. Physiological measures of stress reactivity will include HR, BP, and salivary cortisol consistent with previous studies from our group. Saliva samples will be collected before and after in swabs using the Cortisol-Salivette® system (Sarstedt) and measured using the Cortisol ELISA Kit (Enzo Life Sciences), per manufacture instructions. Subjective stress will be assessed before and after using a single-item VAS question (see below) and HR/BP will also be collected before during and after the CPT.

**Stress (Self-Report).** Subjective stress levels will be assessed with the DASS-21, a validated and reliable measure of core symptoms associated with depression, anxiety and stress. We will also use a Visual Analogue Scale (VAS) ("Please rate your current stress level": 0=no stress, 10=extreme stress) to assess current subjective stress levels. These measures will be collected on each test day prior to the laboratory tasks.

**Cue Reactivity/Craving (LPP).** The late positive potential (LPP) is an event-related potential component thought to reflect the motivational relevance of visual stimuli. The LPP to drug images is enhanced in drug users compared to controls, is correlated with craving, and tracks with abstinence, thus serving as an objective measure of cue reactivity/cue-induced craving. EEG will be collected on test days prior to the cold pressor task. The Picture Viewing Task will be used to elicit the LPP. Suvorexant might lead to decrease drug use through reducing reactivity toward drug cues. Therefore, the picture viewing task will provide this neural assessment of cue reactivity. In the task, the participants view images in four categories, pleasant, unpleasant, methamphetamine, and neutral. The other image categories are necessary, so that we can ensure the brain reactivity is specifically in response to drug images and not just salient images. This is a standard task used in the EEG literature and a meta-analysis shows drug users have an increased

response to drug images with a large effect size.

**Cue Reactivity/Craving (Self-Report).** The Brief Substance Craving Scale (BSCS) will be used to assess current MA craving. The BSCS will be assessed on each test day prior to laboratory tasks.

**Safety/Side Effects.** A 31-item questionnaire will be administered on each test day to assess side effects and adverse events. The Colombia Suicide Severity Rating Scale (CSSRS) and Beck's Depression Inventory (BDI) will be administered at each visit per NIH guidelines. Breath alcohol concentration will also be assessed at each visit to assess for current intoxication.

**EEG Protocol.** On EEG days, participants will be seated comfortably in front of a monitor, fitted for the EEG cap, and the electrodes will be prepared with conductive gel. EEG will be collected using a 64-channel actiCAP electrode cap, amplified with BrainAmp MR and digitized using Brain Vision Recorder (Brain Products, Munich). The EEG machine is situated within the CNRA on the first floor of the Behavioral and Biomedical Sciences Building. Before collection, impedances will be maintained below 50 k(OHM), as suggested by the manufacturers. The sampling rate will be 250 Hz and data will be filtered with .1 Hz high-pass and 100 Hz low-pass filters. Resting State EEG. Resting state EEG will be collected prior to the Picture Viewing Task (below). We will collect resting EEG for 3 minutes with eyes opened and 3 minutes with eyes closed. Picture Viewing Task. The Picture Viewing task will be used to elicit the LPP, reflecting the motivational salience of a stimulus. During this task, participants are asked to view a slideshow of images including pleasant, unpleasant, neutral, and MA-related images. EEG Data Reduction. Data reduction will be performed with Brain Vision Analyzer 2, MATLAB, and BESA. Resting state data will be analyzed using the fast-Fourier transform. The primary outcome of interest will be alpha power (8-12Hz) although other frequencies will also be explored. Picture Viewing Task data will be segmented (200 ms pre-stimulus to 1000 ms post-stimulus) by the following conditions: unpleasant, pleasant, methamphetamine, and neutral images. The LPP will be defined as the mean amplitude between 400-800ms post stimulus over an ROI of central-parietal electrodes used in prior reports.

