### Primary Hypotheses and Specific Aims:

Primary Aim 1: Determine the effects of SUVO on sleep, stress, and cue reactivity/craving

Hypothesis 1a: SUVO compared to placebo will improve sleep outcomes assessed by actigraphy (total sleep time, wake after sleep onset), self-report (Pittsburg Sleep Quality Index), and EEG (resting state alpha power);

Hypothesis 1b: SUVO compared to placebo will improve acute stress reactivity as measured by physiological responses (cold-pressor task induced cortisol and HR/BP) and subjective ratings (Visual Analog Scale; Depression Anxiety Stress Scale).

Hypothesis 1c: SUVO compared to placebo will reduce cue reactivity/craving as measured by LPP to methamphetamine images and self-report (Brief Substance Craving Scale).

Exploratory Aim 2: Evaluate the preliminary safety and side effects profile of SUVO.

**Primary outcome measures:** self-reported sleep, resting state alpha power, LPP, self-reported stress, and cortisol measured at each study visit after 1-week of SUVO, washout, and PL; total sleep time and wake after sleep onset measured nightly via actigraphy watch

**Secondary outcome measures:** methamphetamine use (TLFB and UDS) measured at each study visit after 1-week of SUVO, washout, and PL; side effects questionnaire, BDI, and CSSRS measured at each study visit after 1-week of SUVO, washout, and PL

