## Methods:

**Overall study design.** We will use a two-group cross-over design. Each group will complete three conditions, each lasting one week. 12 participants will be randomized to one of the two groups. Group one (n=6) will receive one-week placebo, one-week washout, and one-week SUVO. Group two (n=6) will receive one-week SUVO, one-week washout, and one-week placebo. During the washout period, the participants will not receive any pills. Eligibility criteria and baseline measures will be collected on Day 0 before the start of week one. Participants will come to the clinic once a week on Monday for 4 weeks. On Day 1 (Monday) of the first week, the participants will receive their medication and actigraphy watches. Each following Monday, they will complete self-report and drug use measures, as well as the laboratory tasks (cold pressor and EEG). Table 1 outlines the schedule of assessments. We will aim to enroll a total of 16 participants to complete 12, with dropouts being replaced, if possible.

**Participants, Recruitment, and Setting.** The participants will consist of non-treatment-seeking individuals meeting DSM-5 criteria for MA use disorder. All participants will be between the ages of 18-45 and fluent in English. IRB NUMBER: HSC-MS-22-0796 IRB APPROVAL DATE: 10/09/2023

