Individuals will be excluded if they meet the following criteria: presence of an alcohol use disorder (AUD), reporting binge drinking (>7 drinks for women and >14 drinks for men), greater than mild substance use disorder on any other illicit drug; any medical conditions contraindicating SUVO (e.g., severe pulmonary disease, severe cardiovascular disease or clinically abnormal ECG, severe liver or kidney disease, seizure disorder, or sleep disorder – particularly narcolepsy); currently taking medications with known drug interactions with SUVO (e.g., MAO inhibitors, anticonvulsants, haloperidol, phenothiazines, anesthetics, and any sedative); pregnant or breast feeding; current DSM-5 psychiatric disorder or neurological disease requiring on-going treatment that would make participation unsafe; history of seizure disorder; head injury with loss of consciousness in the last 5 years. Eligibility criteria will be assessed at baseline and will be conducted by licensed counselors and the medical director ([name]). The study will be conducted at the Center for Neurobehavioral Research on Addiction (CNRA), where the PI ([name]) and Co-Is (Drs. [name], [name], [name]) have experience conducting treatment and laboratory-based studies in substance use populations. Recruitment will follow typical CNRA protocols, including local advertising in print/radio, recruitment companies (Build Clinical/TrialFacts) and referrals from prior CNRA studies and the Houston area. Data analyses will be performed by [name], a biostatistician also affiliated with the CNRA, with expertise in the application of quantitative methods to investigate experimental and clinical outcomes related to EEG, sleep, and psychostimulant use.

	0 (Intake)	1 (PL or SUVO)						2 (washout)						3 (PL or SUVO)						4 (Final)			
		M	T	W	R	F	S	S	M	T	W	R	F	S	S	M	T	W	R	F	S	S	
Study Day	M-F																						M
Consent and Baseline Screening (UDS, SCID, ASI, KMSK, TLFB, physical/ psychiatric eval)	x																						
Receive Study Medication (SUVO or PL)		x	x	x	x	x	x	x								x	x	x	x	x	x	x	x
Medication Compliance		x	x	x	x	x	x	x								x	x	x	x	x	x	x	x
Actigraphy		x	x	x	x	x	x	x	x	x	x	x	x	x	x	x	x	x	x	x	x	x	x
Self-report Sleep, Stress, Craving, MA use (PSQI, ISS, PROMIS-SF, DASS, VAS, BSCS, BDI, TLFB), and UDS									x							x							x
Laboratory Tasks (Cold Pressor, EEG)									x							x							x

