**SCID** - Structured Clinical Interview for DSM-5, **ASI** - Addiction Severity Index; **KMSK** - Kreek-McHugh-Schluger-Kellogg scale; **TLFB** - Timeline Followback; **PSQI** – Pittsburg Sleep Quality Index; **ISS** – Insomnia Severity Index; **PROMIS-SF** – Patient Reported Outcomes Measurement Information System Short Form Sleep Disturbance; **BDI** – Beck’s Depression Inventory; **DASS** – Depression Anxiety Stress Scale; **VAS** – Visual Analogue Scale of Stress; **BSCS** – Brief Substance Craving Scale.

**Payment and Compensation.** Participants will receive \$40 for the baseline evaluation. As methamphetamine users tend to live further outside the city, we are budgeting extra for bus/parking validation/rideshare options, up to \$30 per visit. Participants will receive \$50 for each laboratory visit (3 visits total) and a completion bonus on their final visit for \$50. If medication compliance is reached, participants will receive an extra \$10 at each clinic visit (for more information see Medication Compliance).

**Baseline Screening.** As a part of the CNRA general evaluation protocol (HSC-MS-0322), participants will receive a full physical and psychiatric evaluation on the first day including: a medical-history questionnaire, physical examination, urine drug screen (UDS), pregnancy test, blood draw, and ECG. Clinicians will administer the SCID, the ASI, the KMSK, and TLFB to assess current diagnoses, severity, chronicity, and daily use of MA (Table 1). UDS will be used to assess eligibility and substance use at baseline as well as on EEG testing days. It will also be used to assess medication compliance.

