### Data Analytic Strategy:

**Overview.** Analyses will primarily rely on generalized linear modeling (GLM) for cross-sectional analyses and generalized linear mixed modeling (GLMM) for longitudinal analyses. This approach allows for various outcome distributions and multilevel data. All models will account for repeated observations with via the best-fitting structure of level-2 intercepts/slopes. We will aim to collect full data on 12 participants. Other participants who drop out or are withdrawn will be excluded from analyses, depending on how much data we are able to collect. If only a few data points are missing, generalized linear mixed modeling will natively handle missing outcome data. GLMM natively handles missing data by allowing unequally spaced observations between participants; any other issues related to missing data will be handled via explicit modeling of missingness or imputation. Analyses will be performed in R^72 via packages lme4, rstan, and brms. **Confounders:** Preliminary data analyses will inspect relationships between sample characteristics, predictors, and outcomes via GLMM. Variables that demonstrate a relationship with both the predictor and outcome in a model meet criteria for being potential confounders and yield models with and without covariate adjustment. We report the simpler model if inferences are not affected by these covariates and report both models otherwise.

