### Specific Hypothesis Testing.

**Aim 1:** GLMM for repeated measures will separately model each outcome measure as a function of treatment condition, with Level-2 effects included for best fit. Outcomes will include measures of sleep (H1a: actigraphy; self-report sleep quality; EEG), acute stress reactivity (H1b: physiological responses; subjective ratings) and cue reactivity/craving (H1c: LPP to methamphetamine images; self-report craving)

**Aim 2:** Descriptive statistics will evaluate the frequency of adverse events (AEs) and severe adverse events (SAEs) between and within conditions. Logistic regression will evaluate presence (vs. absence) of specific AEs as a function of condition.

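### No pre-dose use of the side-effect form is named and Aim 2 has no new-since-entry rule, so raw adverse-event frequencies within each condition can include symptoms present at entry

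*Combined protocol and SAP*

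**What the plan says.** **Timing of the form.** Under Measures, Safety/Side Effects: "A 31-item questionnaire will be administered on each test day to assess side effects and adverse events". The secondary outcomes under Primary Hypotheses and Specific Aims list "side effects questionnaire, BDI, and CSSRS measured at each study visit after 1-week of SUVO, washout, and PL". Methods, Overall study design, has medication handed out on Day 1, and then: "Each following Monday, they will complete self-report and drug use measures, as well as the laboratory tasks (cold pressor and EEG". Test days therefore fall one, two and three weeks after medication is first handed out.

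**Intake.** The form has no row in Table 1. The intake row reads "Consent and Baseline Screening (UDS, SCID, ASI, KMSK, TLFB, physical/ psychiatric eval", and the Baseline Screening paragraph adds "a medical-history questionnaire, physical examination, urine drug screen (UDS), pregnancy test, blood draw, and ECG". Overall study design also mentions baseline measures on Day 0 without itemising them, and Baseline Screening refers to a separate evaluation protocol that is not part of the documents.

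**Analysis.** Specific Hypothesis Testing, Aim 2: "Descriptive statistics will evaluate the frequency of adverse events (AEs) and severe adverse events (SAEs) between and within conditions". A logistic regression then models whether each specific event is present or absent by condition. No rule covers a symptom that was there at entry, and the plan does not say whether an event means an item on the form or an entry in the Adverse Event Log.

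**Safeguards.** Adequacy of Protection Against Risks and the Data Safety and Monitoring Plan provide for a log that records duration, severity, frequency and relationship to study drug. The former section also provides for weekly review of adverse events and regular evaluation by the study physician.

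**The concern.** Active methamphetamine users are likely to arrive with symptoms that a side-effect form would pick up. The Background links chronic use and withdrawal to poorer sleep, and Potential Risks names somnolence among the commonest reactions to suvorexant. If the form is first completed after a week of study medication, a symptom carried in from before entry looks the same as one that began on treatment. Both would count towards that condition's frequency.

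What is at stake is the set of raw frequencies that Aim 2 will report as a preliminary side-effect profile. The Medication section calls this the first study of suvorexant in this population, so later readers may take those percentages at face value. A pre-dose rating cannot be obtained once dosing has begun.

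**Working it through.** The plan states no figure on this point. The check is a reading of the schedule, followed by an illustration.

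**1. What each sequence has on the same form** (Overall study design and Table 1, n=6 planned per group)

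| Sequence | First Monday rating | Second | Third | Rated before suvorexant? |
|---|---|---|---|---|
| Placebo first | after placebo | after washout | after suvorexant | Yes, twice |
| Suvorexant first | after suvorexant | after washout | after placebo | None named |

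As written, 6 of 12 completers have no named rating on the form before suvorexant. The other 6 have two, but no rule uses either as a reference. This rests on the form not being given on Day 0, which the documents suggest but do not settle.

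**2. Illustration of the inflation** (every rate is an assumption)

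Inputs for one symptom: entry prevalence p = 0.10, 0.25 or 0.40; share s of those still reporting it at the rating = 0.25, 0.50 or 1.00; onset in everyone else 0.25 on suvorexant and 0.05 on placebo.

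- Carried in: c = p × s
- Reported frequency: f = c + (1 − c) × onset
- Share of reports present at entry: c / f
- Crude gap: (0.25 − 0.05) × (1 − c) = 0.20 × (1 − c)

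Worked case, p = 0.25 and s = 0.50: c = 0.125. Suvorexant f = 0.125 + 0.875 × 0.25 = 0.344, share 0.125/0.344 = 0.36. Placebo f = 0.125 + 0.875 × 0.05 = 0.169, share 0.125/0.169 = 0.74. Of 12 people that is 4.1 and 2.0 reports, with 1.5 carried in under each condition.

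| s | p | c | Suvorexant f (share) | Placebo f (share) | Gap |
|---|---|---|---|---|---|
| 0.25 | 0.10 | 0.025 | 0.269 (0.09) | 0.074 (0.34) | 0.195 |
| 0.25 | 0.25 | 0.0625 | 0.297 (0.21) | 0.109 (0.57) | 0.188 |
| 0.25 | 0.40 | 0.10 | 0.325 (0.31) | 0.145 (0.69) | 0.180 |
| 0.50 | 0.10 | 0.05 | 0.288 (0.17) | 0.098 (0.51) | 0.190 |
| 0.50 | 0.25 | 0.125 | 0.344 (0.36) | 0.169 (0.74) | 0.175 |
| 0.50 | 0.40 | 0.20 | 0.400 (0.50) | 0.240 (0.83) | 0.160 |
| 1.00 | 0.10 | 0.10 | 0.325 (0.31) | 0.145 (0.69) | 0.180 |
| 1.00 | 0.25 | 0.25 | 0.438 (0.57) | 0.288 (0.87) | 0.150 |
| 1.00 | 0.40 | 0.40 | 0.550 (0.73) | 0.430 (0.93) | 0.120 |

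**3. What happens to the comparison**

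With no entry symptoms the gap would be 0.20. Here it is 0.12 to 0.195: diluted, but in the same direction. If the same people carry the symptom through both weeks and onsets are independent, the paired odds ratio is (0.25 × 0.95)/(0.05 × 0.75) = 6.33 whatever c is, because carriers report under both conditions and drop out of the discordant pairs.

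**4. Non-completers**

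The plan says: "We will aim to enroll a total of 16 participants to complete 12, with dropouts being replaced, if possible". That allows 16 − 12 = 4 dropouts. How many would be suvorexant-first is unknown (0 to 4; 2 if split evenly). Those who leave before the placebo week lack that comparator, though anyone who reaches the washout visit has an off-drug rating. Whether they are analysed is open: "Other participants who drop out or are withdrawn will be excluded from analyses, depending on how much data we are able to collect".

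**The case against.** The best defence has three parts.

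*The form may be given at intake after all.* The secondary-outcome wording uses the same post-week phrase for TLFB and UDS, and both are also collected at intake, so the phrase does not exclude a baseline. Table 1 also omits the CSSRS and breath alcohol, which Measures requires at every visit, so a missing row proves little. This stands as a reason for caution. It does not supply a pre-dose rating, and the missing rule in Aim 2 would remain even if the form were given on Day 0.

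*Clinical review would sort out old symptoms.* Intake history and examination, log duration, relatedness ratings and physician review could all identify a pre-existing complaint. These are real partial safeguards. Aim 2 does not say that any of them decides what is counted.

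*The crossover supplies the control.* For completers this is right, and it limits the point to raw frequencies in an exploratory aim.

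A reader might infer more than the documents support:

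- That the safety comparison of suvorexant with placebo is invalid. It is not. With six completers per sequence, each condition is rated equally often in the first and last week, and carried-in symptoms tend to appear on both sides.
- That the inflation sits mainly in the first period. The illustration applies one persistence value to both conditions, although half of each condition's ratings come about three weeks after entry. It says nothing about concentration by period.
- That there is no baseline safety assessment. There is one; what is not named is an itemised pre-dose rating on the same form.

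**Conclusion.** The point holds in a limited form. Followed as written, the plan names no pre-dose use of the 31-item form and no new-since-entry rule, so symptoms present at entry can inflate the raw frequencies reported within each condition. The first half is uncertain because Day 0 content is not itemised and the screening protocol cannot be seen. The second half is plain from Aim 2.

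The size is unknown. Over the assumed grid, the share of reports already present at entry runs from 9% to 73% on suvorexant and from 34% to 93% on placebo. These figures show what could happen and are not estimates. It would be smaller if events are taken from the log after clinical review, which the plan does not settle.

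The suvorexant-placebo comparison in completers remains interpretable through the placebo week, and Aim 1 does not depend on the form. This is a cheap, low-priority improvement.

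**What to change.** - Give the 31-item form once before the first dose, on Day 0 or on Day 1 before medication is handed out, and add a row for it to Table 1. If it is already given then, the row alone settles the matter.
- In Aim 2, report frequencies by condition in two columns: all reports, and reports new relative to the pre-dose rating. Count worsening as well if the form grades severity; the plan does not say that it does.
- While editing Aim 2, it would help to state whether an event is a form item or a log entry. This is a clarification, not a condition of the fix.

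Cost: at an assumed 5 to 10 seconds per item, 31 × 5/60 = 2.6 to 31 × 10/60 = 5.2 minutes per participant at a visit that already takes place, plus one table column. Sample size and power do not change. The drawback is that one pre-dose rating in active users may shift with recent methamphetamine use, and a new-only count can hide a symptom that the drug keeps going. The all-reports column is kept for that reason.
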